11.2.3. The Method of Handling Missing Value and Outliers

Every effort will be undertaken to minimize missing or incorrect data. However, some missingness is inevitable. The reasons for missing or incorrect data will be described in detail and evaluated for assessment of possible bias if appropriate. The distribution of missing and/or

incorrect data will be analyzed too, which will be separately analyzed based on whether the data is collected prospectively or not.

For the missing data, only the missing primary endpoint indicators will be carried forward during analysis, and the specific carry forward method will be explained in SAP. Sensitivity analyses will be performed on the primary safety and effectiveness endpoints to assess the impact of missing data on study results. In addition to worst-case missing data filling, Tipping Point Analysis will be performed as a post-hoc Analysis to assess the impact of different missing data filling methods on the results.

Error and unreasonable data will be checked and confirmed during data cleansing prior to statistical analysis. Error data will be corrected before analysis, and sensitivity analyses will be performed to assess the impact of unreasonable data on the stability of the results if appropriate.

11.2.4. Number of Subjects per Investigative Site

Thirty ATTEMPT or TREATMENT subjects will be enrolled from one site.

11.3. Data Analyses.

11.3.1. Primary Endpoints/Measurements

The primary safety and effectiveness endpoints will be analyzed after all the enrolled subjects finishing One-month Visit data collection. The primary safety endpoint will be analyzed for ATTEMPT and TREATMENT subjects in ITT set. The primary effectiveness endpoint will be analyzed for TREATMENT subjects in mITT set. Descriptive statistics will be conducted for the effectiveness endpoint events. The number, incidence (amount of events/number of subjects) and its 95% confidence interval will be calculated (exact methods). Explorative statistical analysis might be produced if appropriate, e.g., Bayesian estimation of the study results using FARAPULSE IDE data as the prior.

11.3.2. Secondary Endpoints/Measurements

The primary safety and effectiveness endpoints will be analyzed after all TREATMENT subjects finishing Twelve-month Visit data collection. The secondary safety endpoint will be analyzed for ATTEMPT and TREATMENT subjects in ITT set. The secondary effectiveness endpoint will be analyzed for TREATMENT subjects in mITT set and ITT set respectively. Descriptive statistics will be conducted for the effectiveness endpoint events. The number, incidence (amount of events/number of subjects) and its 95% confidence interval will be calculated (exact methods). The final report will be finished then.

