9.4.3. ATTEMPT

An ATTEMPT subject is one who signs informed consent, meets eligibility criteria, and has any study device inserted into the body but does not receive ablation (PFA energy) with the FARAPULSE Pulsed Field Ablation System for PVI. ATTEMPT subjects will be used for analysis of the primary and secondary safety endpoints and count toward the enrollment ceiling.

The original signed Informed Consent and any relevant documentation must be maintained in the site’s subject file. A subject ID will be assigned in the EDC system. ATTEMPT subjects are not allowed to be re-enrolled in the study.

Prospectively enrolled ATTEMPT subjects will be followed up to 30 days for safety. For

retrospectively enrolled ATTEMPT subjects, one-month follow-up data will be collected. ATTEMPT subjects will not need to complete data collection of the post-procedure arrhythmia. All applicable eCRFs, per the protocol, will be completed.

For ATTEMPT subjects, at the minimum the following forms must be completed:

- Enrollment and baseline forms such as, but not limited to: ICF, enrollment information and other related forms.
- End of Study form.
- Protocol Deviation form
- Adverse Event forms for any reportable event, as defined in Section 18.1 for any adverse event that occurs after signing the ICF, up to the point of subject withdrawal

9.4.4. *TREATMENT*

Any subject that signs the ICF, meets key eligibility criteria and has the specified study device inserted into the body and receives PFA ablation with the FARAPULSE Pulsed Field Ablation system will be classified as “TREATMENT”. The data collection of these subjects will be performed in accordance with the follow-up schedule and are included in all study analyses. A subject ID will be assigned in the EDC system.

All applicable eCRFs, per the protocol, must be completed for TREATMENT subjects. TREATMENT subjects do count towards the enrollment ceiling and will be used for analyses of the endpoints. The original signed ICF and any relevant documentation must be maintained in the center’s patient file.

9.5. *End-of-Study Definition*

A clinical trial is considered completed when the last participant’s last study data collection has occurred.

A subject is considered to have completed the study if he/she has completed all data collection including the last visit or assessment as shown in the Data Collection Schedule shown in **Table 10-1**.

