For subjects undergoing a re-ablation procedure the following data will be collected:

- Date and time of visit, way to collect the data
- Date and time of Re-ablation
- Reason for Re-ablation
- During any re-ablation procedure in which LA access is performed, a mapping procedure is recommended to be performed to characterize the reconnection status for each originally treated PV to characterize lesion durability.
- For subjects who received ablation of the CTI, the persistence of nonconductivity in targeted tissue will be evaluated with either pacing maneuvers or electroanatomical mapping.
- Lesion set data

10.13. *Study Completion*

Each Treatment subject will be followed until the Twelve-Month Follow-Up Visit is completed. The end of the study is defined as completion of the last visit shown in the Data Collection Schedule.

ATTEMPT subjects will be followed up to the One Month Follow-Up Visit. However, ATTEMPT subjects will not need to complete post-procedure arrhythmia monitoring.

Even though a subject's participation in the clinical study has ended, physicians may wish to continue standard of care visits outside of the study.

In case of premature termination of the study, please refer to **Section 9**. Following termination/completion of the study, subjects will be managed according to local institution practice.

Site must complete the "End of Study" eCRF to signify study completion.

10.14. *Unforeseen Circumstances (Natural Disaster/Global Pandemic)*

There may be unforeseen circumstances that occur during the course of the study, such as a natural disaster (e.g., hurricanes, tornadoes) or a global pandemic (e.g., COVID-19) that prevents a subject from attending study visits during the required follow-up window. While every attempt should be made to avoid disruptions in collecting study data, it is important to collect as much data as possible, by any available means and from any available resources. This may include obtaining records from an outside clinic, hospital or other healthcare facility

that is not EC approved.

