11.1.2. Secondary Endpoints

11.1.2.1. Secondary Safety Endpoints

The secondary safety endpoint will evaluate the proportion of subjects that free from primary safety events defined in **Section 6** through 7 days after the procedure and free from the following serious procedure-related and/or device-related adverse events at any time through the completion of 12-month follow-up visit, which will be assessed at the time of the twelve-month analysis:

- Atrial esophageal fistula
- Severe PV stenosis
- Persistent phrenic nerve palsy*

**The study will collect information on phrenic nerve palsy observed before the end of the index procedure and, in case of occurrence, will track information for potential recovery during the study visits.*

11.1.2.2. Secondary Effectiveness Endpoint 1

The first secondary effectiveness endpoint will evaluate the chronic success, which is defined as proportion of subjects that free from effectiveness events defined as failure as below at twelve months post-procedure.

Effectiveness events determining a failure are defined as:

- Fail to achieve electrical isolation of all PVs using FARAPULSE Pulsed Filed Ablation system only.
- After the Blanking Period to 12-month after the procedure:

- a) Occurrence of any Detectable AF, AFL* or AT captured by one of the following methods: ≥ 30 seconds in duration recording from 24-hour or longer Holter Monitor or ≥ 10 seconds recording from 12-lead ECG.
- b) Any cardioversion for AF, AFL* or AT.
- c) Use of any Class I or Class III AADs[#] for the treatment of AF, AFL* or AT.
- At any time through 12 months after the procedure:
 - a) Re-ablation for AF, AFL* or AT.
 - b) Use of amiodarone, except intra-procedurally to control an arrhythmia.

#It won't be considered as a failure if the subject has three-month visit happened after 90 days post the procedure, but still in the window (≤ 104 day) with AADs on, and physicians decide to take AADs off after this visit.

**excluding CTI-dependent flutter confirmed by EP study*

11.1.2.3. Secondary Effectiveness Endpoint 2

The second secondary effectiveness endpoint will evaluate the proportion of PVs that achieve electrical isolation by using the FARAPULSE Pulsed Field Ablation system only.

11.1.2.4. Secondary Effectiveness Endpoint 3

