4.1 Analysis Sets

ITT set will involve subjects who have signed informed consent and satisfied with all key criteria. Primary effectiveness endpoints will be summarized for TREATMENT subjects in mITT set.

Secondary effectiveness endpoints will be summarized for TREATMENT subjects in ITT set and mITT set respectively.

Primary and secondary safety endpoints will be summarized for ATTEMPT and TREATMENT subjects in ITT set.

The additional endpoints will be summarized for TREATMENT subjects in ITT set.

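### The 12-month secondary safety rate includes ATTEMPT subjects, whose follow-up ends at one month, and the plan has no consistent rule for scoring those with no event by then.

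*Protocol*

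**What the plan says.** **Population.** Protocol 11.3.2: "The secondary safety endpoint will be analyzed for ATTEMPT and TREATMENT subjects in ITT set". Protocol 9.4.3 agrees: "ATTEMPT subjects will be used for analysis of the primary and secondary safety endpoints and count toward the enrollment ceiling". So does SAP 4.1: "Primary and secondary safety endpoints will be summarized for ATTEMPT and TREATMENT subjects in ITT set". The protocol synopsis, protocol 11.2.1 and SAP 1 repeat it.

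**Endpoint.** Protocol 6.2.2.2 and 11.1.2.1 and SAP 3.4 define a two-part composite. The subject must have no primary safety event through day 7. The subject must also have no atrio-esophageal fistula, severe PV stenosis or persistent phrenic nerve palsy among serious related "adverse events at any time through the completion of 12-month follow-up visit". Table 6.2-1 defines persistent palsy by its status at the 12-month visit.

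**Follow-up.** Protocol 9.4.3: "Prospectively enrolled ATTEMPT subjects will be followed up to 30 days for safety"; for "retrospectively enrolled ATTEMPT subjects, one-month follow-up data will be collected". Protocol 10.13 confirms it: "ATTEMPT subjects will be followed up to the One Month Follow-Up Visit".

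**Estimator.** Protocol 11.2 and 11.3.2 and SAP 4 divide the number of events by the number of subjects and attach an exact 95% interval. No censoring or time-to-event method is planned. Carry-forward of missing values is limited to primary endpoints (protocol 11.2.3, SAP 7.4). SAP 7.3, straight after a sentence on baseline categorical variables, says that denominators use the patients who complete the visit.

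**The concern.** The population and the follow-up schedule do not fit each other. The endpoint's second part runs to 12 months, but every ATTEMPT subject leaves the study at about one month. This is built into the design and is not loss to follow-up, so better retention would not cure it.

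An ATTEMPT subject with no event by one month adds one to the denominator and nothing to the events, and so counts as a 12-month success without having been observed for 12 months. Three things could go unseen:

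- a late fistula;
- a late stenosis, especially where another catheter completed the case, which protocol 10.5.1.4 allows;
- the eventual status of a palsy still unresolved at one month.

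The data are meant to support registration in China (protocol 4.2 and 7.3). A rate presented as 12-month safety would rest partly on one-month observation, with the scoring left open until the data are known.

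**Working it through.** **Inputs.** Total of 30 ATTEMPT and TREATMENT subjects (protocol 7.1 and 11.2.4). Two-sided 95% exact (Clopper-Pearson) interval (protocol 11.2). The number of ATTEMPT subjects, *k*, is not given; values from 0 to 5 are assumed.

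**1. The plan's own table.** Exact intervals for 0, 1, 2 and 3 events in 30 come to 0–11.6%, 0.1–17.2%, 0.8–22.1% and 2.1–26.5%. All four rows of protocol 11.1.1.1.2 and SAP 3.2.2 are reproduced. That table is stated for the primary safety endpoint; 11.6% is used below only because the same method and n=30 would apply here.

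**2. No events, upper limit for the event rate**, 1 − 0.025^(1/n):

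| *k* | n observed for 12 months | Upper limit |
|---|---|---|
| 0 | 30 | 11.6% |
| 2 | 28 | 12.3% |
| 4 | 26 | 13.2% |

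**3. One TREATMENT event, no ATTEMPT event.** The event-free rate is 29/30 = 96.7% in the stated population. In TREATMENT subjects alone it is 27/28 = 96.4% (*k*=2) or 25/26 = 96.2% (*k*=4).

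**4. Wider range.** For *k* from 1 to 5 and 0 to 3 TREATMENT events, counting event-free ATTEMPT subjects as successes raises the rate by 0 to 2.0 points (at most 90.0% against 88.0%). It raises the lower exact limit by 0.3 points (88.4% against 88.1%) to 4.7 points (73.5% against 68.8%).

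**5. The unstated scoring rule**, *k*=2 and no events:

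| Scoring of the 2 ATTEMPT subjects | Event-free rate (95% interval) |
|---|---|
| Counted as successes | 30/30 = 100% (88.4–100) |
| Dropped | 28/28 = 100% (87.7–100) |
| Counted as failures (worst case) | 28/30 = 93.3% (77.9–99.2) |

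With *k*=5 the worst case gives 25/30 = 83.3% (65.3–94.4). The choice of rule can therefore matter more than the denominator.

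**6. An ATTEMPT subject who fails.** Take *k*=2, one ATTEMPT subject with tamponade by day 7 and no TREATMENT event. The stated population gives 29/30 = 96.7% (82.8–99.9). Removing ATTEMPT subjects altogether gives 28/28 = 100% (87.7–100).

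**The case against.** A reader might infer that ATTEMPT subjects can enter this rate only as event-free, so that including them always flatters the device. The documents do not support that. The composite includes all primary safety events through day 7, for which ATTEMPT subjects are fully followed. One with tamponade or a vascular access complication by day 7, or a fistula or stenosis found by one month, is an observed failure. Step 6 shows that removing ATTEMPT subjects outright could hide such a failure from this endpoint.

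The unobserved part is also narrower than the whole second component. Under the footnote to Table 10.1-1, palsy is followed only when detected at the procedure, so a subject without palsy, or with palsy resolved by one month, is already settled on that item. Table 6.2-1 counts stenosis only in an ablated vein. CT or MRI after the procedure is done on suspicion in TREATMENT subjects too.

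*k* may well be 0 or 1. In the consolidated earlier data (protocol 4.1.3), acute success was 81/81 in a set that included everyone who began the procedure, with a lower limit of 95.5%. The corresponding 4.5% of 30 is 1.35 subjects. At *k*=1 with no events the upper limit is 11.9%.

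Finally, including everyone with a device inserted is a deliberate safety choice, and the study tests no hypothesis.

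All of this limits the size and direction of the problem. It does not remove the conflict: a 12-month rate is defined on a group that has no visit after one month, and the one denominator sentence that might resolve it contradicts the stated population.

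**Conclusion.** The point holds as a structural inconsistency. Both documents put ATTEMPT subjects into a rate that runs to 12 months, and the protocol ends their follow-up at one month. Those with no event by then have an undetermined status that the stated estimator treats as success. SAP 7.3, whose scope is unclear, would drop them if it applied.

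The direction of bias is not fixed, because ATTEMPT subjects with an acute event count as failures. The size is small: with no events, the upper limit moves by 0.7 points (12.3 − 11.6) at *k*=2 and 1.6 points (13.2 − 11.6) at *k*=4, and not at all at *k*=0. These figures rest on assumed values of *k* and on no ATTEMPT subject having an event. No test or threshold depends on the result; what is at stake is whether the 12-month label is accurate and the scoring is fixed in advance.

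**What to change.** In protocol 9.4.3, 11.2.1 and 11.3.2 and SAP 1 and 4.1 (and the matching synopsis lines):

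- report the 7-day component of the secondary safety endpoint in ATTEMPT plus TREATMENT subjects;
- report the 12-month event-free rate in TREATMENT subjects;
- show ATTEMPT safety events through the one-month visit in a separate row beside that rate, so that no acute failure is lost;
- keep ATTEMPT subjects in the primary safety endpoint, unchanged.

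SAP 7.3 should also say whether its denominator sentence covers endpoint rates or only baseline variables.

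In the example at step 6, the report would then show 29/30 for the 7-day component, 28/28 for the 12-month rate, and one event among the two ATTEMPT subjects next to it.

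The cost is wording only, with no new visits or subjects. The 12-month denominator falls by the number of ATTEMPT subjects, and its interval is slightly wider.

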6.2. Study endpoints

6.2.1. Primary Endpoints

6.2.1.1. Primary Effectiveness Endpoint

The primary effectiveness endpoint is the acute procedural success, defined as the proportion of subjects that achieve electrical isolation* of all PVs using FARAPULSE Pulsed Field Ablation system only.

** Electrical isolation of a PV is demonstrated by entrance block after a 20-minute waiting period if the subject is enrolled prospectively, otherwise the way to confirm electrical isolation should be recorded, including whether there is a waiting period and its duration. If exit block testing is performed, the PV will only be considered isolated if both entrance and exit block testing was successful.*

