10.5.1.1. Pulmonary vein isolation

Use of the FARAWAVE Pulsed Field Ablation system should be restricted to those physicians who are specialists trained, experienced in cardiac ablation procedures to treat cardiac arrhythmias, and have been trained with the use of these devices.

Subjects will undergo sedation/anesthesia according to institutional protocol. They will then be prepared in conventional sterile fashion for a cardiac catheterization procedure. Femoral vein access will be obtained via Seldinger technique. A heparin bolus will be delivered prior to or immediately after transseptal puncture. Patients should be anticoagulated to an ACT between 300 seconds to 450 seconds prior to insertion of the FARAWAVE Pulsed Field Ablation Catheter into the blood pool to avoid thrombus formation. A procedural ACT between 300 seconds and 450 seconds should be maintained until all devices are withdrawn from the left atrium. Pre-ablation and post-ablation voltage map are not required. Commercially approved diagnostic catheters may be placed before or after transseptal access is established at the Investigator's discretion. Transseptal access to the LA will be obtained using commercially approved devices, establishing guidewire access to the LA. TEE within 48 hours of the procedure or ICE during the procedure will be utilized prior to transseptal puncture for exclusion of LA thrombus. If the study reveals atrial thrombus, the investigational procedure will not begin or will be terminated, no ablation will be performed, and the subject will be rescheduled. The FARADRIVE Steerable Sheath will be prepared and advanced via guidewire to the LA. The FARAWAVE Pulsed Field Ablation Catheter will then be prepared and advanced to the LA through the FARADRIVE Steerable Sheath. After confirming an ACT of 300 or greater, ablation of the PVs to achieve isolation will be performed according to the approved IFU documents and institutional practice. PVI ablation may be repeated at the Investigator's discretion. Each addressable PV will be ablated in turn.

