10.5.1.4. Additional ablations

CTI ablation: Ablation of the CTI may be performed using any approved catheter in subjects with a past history of CTI-mediated (typical) AFL, subjects who manifest typical AFL during a procedure or within the Blanking Period, or subjects who have inducible typical flutter. Bidirectional block should be demonstrated after the last CTI ablation. The CTI ablation data will be documented in the eCRF and does not constitute a Treatment Failure.

Other Ablation: Other ablation is not permitted under this protocol except when the Investigator determines that subject welfare requires ablation for an accessory pathway, AVNRT, treatment-emergent left AFL or incessant AT, using any approved ablation catheter. This decision and the associated ablation data will be documented in the eCRF and does not constitute an Effectiveness Failure.

If the subject presents with AF after all ablations are complete, cardioversion should be performed and will be noted. Cardioversions during the Index procedure do not signify procedural failures and are not to be reported as adverse events. Induction of or spontaneous conversion to AF during the procedure will not be considered an adverse event. If at any time during the ablation procedure the investigator is unable to continue the ablation with the designated investigational catheter (for the PV isolation), the investigator may consider the case a procedural failure and complete the case with a device determined best for the subject. The point at which failure was determined as well as the rationale must be documented. A protocol deviation will be documented in the EDC system.

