3.2.3 Statistical Methods

Descriptive statistics will be conducted for the safety endpoint events. The number, incidence (amount of events/number of subjects) and its 95% confidence interval (exact methods) will be calculated. The primary safety endpoints will be analyzed for ATTEMPT and TREATMENT subjects in the ITT set. Explorative statistical analysis might be produced if appropriate, e.g., Bayesian estimation of the study results using FARAPULSE IDE data as the prior.

3.3 Secondary Effectiveness Endpoint:

1. Chronic Success: Proportion of subjects that free from effectiveness events defined as failure as below at 12 months post-procedure.

Effectiveness events determining a failure are defined as:

- Fail to achieve electrical isolation of all PVs using FARAPULSE Pulsed Field Ablation system only.
- After the Blanking Period (90 days post the procedure) to 12-month after the procedure
 - a) Occurrence of any Detectable AF, AFL* or AT captured by one of the following methods: ≥ 30 seconds in duration recording from 24-hour Holter Monitor or ≥ 10 seconds recording from 12-lead ECG, or
 - b) Any cardioversion for AF, AFL* or AT, or
 - c) Use of any Class I or Class III AADs[#] for the treatment of AF, AFL* or AT.

- At any time through 12 months after the procedure:
 - a) Re-ablation for AF, AFL* or AT, or
 - b) Use of amiodarone, except intra-procedurally to control an arrhythmia.
- 2. Proportion of PVs that achieve electrical isolation by using the FARAPULSE Pulsed Field Ablation system only.
- 3. Chronic success allowing AADs.

#It won't be considered as a failure if the subject has three-month visit happened after 90 days post the procedure, but still in the window (<=104 day) with AADs on, and physicians decide to take AADs off after this visit.

**excluding CTI-dependent flutter confirmed by EP study.*

3.4 Secondary Safety Endpoint:

Proportion of subjects that free from primary safety events defined as above through 7 days after the procedure and free from the following serious procedure-related and/or device-related adverse events at any time through the completion of 12-month follow-up visit.

- Atrial oesophageal fistula
- Severe PV stenosis
- Persistent phrenic nerve palsy*

**The study will collect information on phrenic nerve palsy observed before the end of the index procedure and, in case of occurrence, will track information for potential recovery during the study visits.*

3.5 Additional Endpoints:

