4. GENERAL STATISTICAL METHODS

Descriptive statistics will be conducted for the primary, secondary and other endpoint events. When descriptive statistics are used, continuous variables will be summarized using standard quantitative statistics: number of available observations, mean, standard deviation, median, quartiles and range (minimum and maximum observed values) and its 95% confidence interval. Categorical variables will be summarized using the number, incidence (amount of events/number of subjects) and its 95% confidence interval (exact methods).

Explorative statistical analysis might be produced if appropriate, e.g., Bayesian estimation of the study results using FARAPULSE IDE data as the prior.

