7.3. Rules and Definitions

For baseline categorical variables, subjects with missing values will not be counted in the corresponding denominators for proportions. Number of patients completing the visit will be considered in denominators.

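### Secondary effectiveness endpoint 2 counts veins, but the only stated interval is a per-subject exact one that takes no account of several veins in one patient

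*Protocol*

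**What the plan says.** Protocol 11.1.2.3 defines the endpoint: it "will evaluate the proportion of PVs that achieve electrical isolation by using the FARAPULSE Pulsed Field Ablation system only". SAP 3.3, item 2, restates it: "Proportion of PVs that achieve electrical isolation by using the FARAPULSE Pulsed Field Ablation system only". SAP 3.3 has no methods text, although both primary endpoints have a methods subsection (SAP 3.1.3 and 3.2.3).

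The estimator for all secondary endpoints is in Protocol 11.3.2: "The number, incidence (amount of events/number of subjects) and its 95% confidence interval will be calculated (exact methods"). The general rule is the same in Protocol 11.2 and in SAP 4: "Categorical variables will be summarized using the number, incidence (amount of events/number of subjects) and its 95% confidence interval (exact methods"). Neither document mentions correlation within a patient.

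Four other places bear on the point:
- Acute success, the primary effectiveness endpoint, is electrical isolation "of all PVs using FARAPULSE Pulsed Field Ablation system only" (Protocol 6.2.1.1). Table 6.1-1 presents endpoint 2 as the per-vein view of acute procedural success.
- If the study catheter cannot be used further, "the investigator may consider the case a procedural failure and complete the case with a device determined best for the subject" (Protocol 10.5.1.4).
- Isolation is recorded for each PV (Protocol 10.5.2).
- Endpoint 2 is summarised for TREATMENT subjects in ITT and mITT, but acute success only in mITT (Protocol 11.2.1, SAP 4.1).

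**The concern.** A formula of events over subjects fits the per-subject endpoints but not a proportion of veins. An analyst will put veins in both numerator and denominator and then apply the exact method that the plan names. That method assumes independent units. Veins of one patient share anatomy, operator and catheter, and Protocol 10.5.1.4 describes a direct route by which several fail together.

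The stake is reported precision. With no hypothesis test, estimates and intervals are the study's whole output, and they are meant to support registration in China (Protocol 7.3). Which veins enter the denominator is also not written down, including how a common trunk counts, although common and middle PVs are admissible in mITT (Table 8.3-1).

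**Working it through.** **1. The plan's own figures.** The exact table for n = 30 (Protocol 11.1.1.1.2, SAP 3.2.2) is Clopper-Pearson, with lower limit B(0.025; x, n-x+1) and upper limit B(0.975; x+1, n-x), where B is the beta quantile. For 0, 1, 2 and 3 events this gives 0-11.57%, 0.08-17.22%, 0.82-22.07% and 2.11-26.53%, which agrees with the table. It is a subject-level table; the plan gives no figure for endpoint 2.

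**2. Assumptions.** 30 TREATMENT subjects with 4 veins each, 120 veins. The documents give neither a vein count nor an intraclass correlation (ICC).

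**3. One switched case.** The study catheter is abandoned after the first vein of one patient, and the other three veins are finished with another device.
- Estimate: 117/120 = 97.5%. Exact on veins: 92.9-99.5%.
- ANOVA ICC from failure proportions (0.75 in one patient, 0 in 29, mean 0.025):
  - MSB = 4 x (0.725² + 29 x 0.025²)/29 = 2.175/29 = 0.075
  - MSW = 4 x 0.75 x 0.25/90 = 0.00833
  - ICC = (0.075 - 0.00833)/(0.075 + 3 x 0.00833) = 0.67
- Design effect = 1 + 3 x 0.67 = 3, so the effective n is 120/3 = 40, with 39 isolated.
- Exact on 39/40: 86.8-99.9%.

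**4. Four failed veins, 116/120 = 96.7%.** The vein-level interval is the same wherever the failures fall.

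| Pattern of failures | Exact on veins | Design effect | Effective n | Adjusted interval |
|---|---|---|---|---|
| One in each of four patients | 91.7-99.1% | 1 (floored) | 120 | 91.7-99.1% |
| Two in each of two patients | 91.7-99.1% | 1.96 | 61.1 | 88.6-99.6% |
| Four in one patient | 91.7-99.1% | 4 | 30 | 82.8-99.9% |

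**5. Average coverage of the vein-level exact interval** (beta-binomial simulation, nominal 95%).

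| True vein rate | ICC 0.1 | ICC 0.3 | ICC 0.5 |
|---|---|---|---|
| 95% | 93.9% | 87.6% | 80.8% |
| 97% | 97.7% | 95.3% | 93.1% |
| 98% | 97.6% | 95.3% | 93.0% |
| 99% | 98.2% | 96.1% | 94.8% |

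The design-effect interval covers 96.2%, 94.4% and 92.5% at a true rate of 95%, and about 99% at 97% or more.

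**6. All veins isolated.** 120/120 has a vein-level lower limit of 97.0%. The same data as subjects, 30/30, have a lower limit of 88.4%. The ICC cannot be estimated from such data, so they do not show where between these two values the right limit lies.

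**The case against.** The strongest objection is that the harm lies outside the likely range. The trials summarised in Protocol 4.1.3 all report 100% acute success (40/40 and 81/81). Serious under-coverage appears only near a true vein rate of 95%, which in this model means per-subject acute success of about 84-90%. This stands and limits the point. It does not rescue the interval in a particular dataset where one case fails on several veins, nor the 97.0% limit when nothing fails.

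A second objection concerns the remedy. The design-effect interval gives a lower limit of 95.4% for 119/120, while the subject-level fallback gives 88.4% for 120/120, so a perfect result carries the worse bound. Its ICC rests on a handful of failures. This also stands: no single interval should be prescribed.

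A reader might infer more than the documents support:
- That the plan would report veins per subject, such as 116/30 = 3.87. The endpoint definition plainly implies veins in the denominator.
- That veins finished with another device could be dropped, turning 117/120 into 117/117 = 100%. Both endpoint definitions require the study system only, and Table 6.1-1 ties endpoint 2 to acute success, so such veins are most naturally failures. The line "Each addressable PV will be ablated in turn" is procedural text in a workflow that Protocol 10.5.1 calls adjustable; it is not an endpoint definition.
- That SAP 7.3 requires patient denominators here: "Number of patients completing the visit will be considered in denominators". That sentence follows one on baseline categorical variables and need not govern endpoint 2.
- That endpoint 2 is the only evidence on acute isolation in ITT. Chronic success, also analysed in ITT, counts failure to isolate all PVs as a component.

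**Conclusion.** The stated estimator does not match endpoint 2, and its natural vein-level version assumes an independence that the design does not have. In a plausible single-case failure the lower limit is 92.9% where about 86.8% is appropriate. With four failures in one patient it is 91.7% against 82.8%. On average the loss is small at true rates of 97% or more (coverage about 93-98%).

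The sizes rest on an assumed 30 x 4 veins and on assumed failure patterns or ICCs. The study is descriptive, so no test, sample size or decision changes. The point is a minor correction, worth making because it is cheap and the vein-level data are already collected.

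**What to change.** In SAP 3.3 and 4:
- **Denominator.** All PVs present in TREATMENT subjects, taken from baseline CT/MRI (Protocol 10.4) or, failing that, the procedure record. Veins not reached, or finished with another device, count as not isolated. State one rule for counting a common trunk.
- **Interval.** Replace the vein-level exact interval with one prespecified subject-clustered interval that stays within 0-100%. A design-effect-adjusted exact interval is one option. A plain Wald cluster-robust interval is unsuitable: it gives 92.1-101.2% for the two-plus-two pattern and 90.1-103.2% for four in one patient.
- **Companion result.** Report subject-level acute success with its exact interval beside endpoint 2 in both ITT and mITT.
- **No failures.** Give the vein count with the subject-level exact interval, labelled as a conservative bound (lower limit 88.4% for 30/30), and do not present the vein-level 97.0% as the precision.

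The cost is a few SAP sentences, standard code and one added ITT line; no new data are needed. The price is a wider, somewhat conservative interval. With the design-effect version, mean width at ICC 0.3 rises from 8.4 to 11.7 points at a true rate of 95%, and from 5.7 to 9.2 points at 98%. The clustering estimate will be unstable with few failures.
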